5.2. Exclusion Criteria

Participants are excluded if any of the following apply:

Medical Conditions

- 15. Have visceral crisis, lymphangitic spread, or leptomeningeal carcinomatosis. Visceral crisis is not the mere presence of visceral metastases but implies severe organ dysfunction as assessed by symptoms and signs, laboratory studies, and rapid progression of the disease.
- 16. Have symptomatic or untreated central nervous system (CNS) metastasis. Participants with treated CNS metastases are eligible if
 - a. "...($\leq \bullet \circ \ldots \geq$ (' ("...z (2' $\leq \circ \geq$ ' "($z \geq z$ ' ($z \geq \ldots \leq$) ("...3(AQ $\geq z$ (prior to first dose of study treatment, and
 - b. they have not received corticosteroids and/or anticonvulsants for at least 14 days prior to first dose of study treatment, and
 - c. their disease is both asymptomatic and radiographically stable by repeat imaging for at least 28 days prior to consent (repeat imaging should be performed during study screening).
- 17. Have a history within the last 12 months of any of the following conditions: syncope of cardiovascular etiology, ventricular arrhythmia of pathological origin (including, but not limited to, ventricular tachycardia and ventricular fibrillation), or sudden cardiac arrest. Exception: patients with controlled atrial fibrillation for >30 days prior to randomization are eligible.
- 18. Have serious preexisting medical condition(s) that, in the judgment of the investigator, would preclude participation in this study (such as severe renal impairment [for example, estimated creatinine clearance <30 mL/min], active symptoms of ILD/pneumonitis, severe dyspnea at rest or requiring oxygen therapy, history of major surgical resection

- 19. Have a history of any other cancer (except nonmelanoma skin cancer or carcinoma in-situ of the cervix), unless in complete remission with no therapy for a minimum of 3 years
- 20. Have a known active systemic infection (for example, bacterial, fungal, or detectable viral infection requiring systemic therapy).
 - a) Participants with uncontrolled human immunodeficiency virus (HIV) infection or an acquired immunodeficiency syndrome (AIDS) defining illness are not eligible.
 Participants with known HIV infection and CD4+ T-≤. A(2TUC53(≤ (BD, (cells/µL are eligible.
 - b) Participants with hepatitis B are not eligible unless viral load is below the level of quantification.
 - c) Participants with known hepatitis C are not eligible unless they have completed curative anti-viral therapy and viral load is below the level of quantification.
 - d) Screening for HIV, coronavirus disease 2019 (COVID-19), hepatitis B, or hepatitis C is not required.

Prior/Concomitant Therapy

- 21. Have received any intervening line of systemic therapy between disease recurrence/progression and study screening.
- 22. Have received more than 1 line of therapy for advanced or metastatic disease.
- 23. Have received prior treatment with chemotherapy for MBC.
- 24. Have received prior treatment with any CDK4 & 6 inhibitor-based regimen other than those specified. Prior treatment with a CDK4 & 6 inhibitor in more than 1 setting (e.g., adjuvant and then metastatic) is not permitted.
- 25. Have received prior treatment with fulvestrant, any investigational ER-directed therapy (including SERDs and non-SERDs), any PI3K-, mTOR-, or AKT-inhibitor.
- 27. Have initiated bisphosphonates or approved RANK ligand (RANK-L) targeted agents (e.g. denosumab) <7 days prior to randomization.
- 28. Are receiving concurrent exogenous reproductive hormone therapy (for example, birth control pills, hormone replacement therapy, or megestrol acetate). Appropriate washout ...' ≥(•........................(\varnow (\varnow \varnow (z \varnow
- 29. Have received an autologous or allogeneic stem cell transplant.

Prior/Concurrent Clinical Study Experience

30. Are currently enrolled in any other clinical study involving an investigational product or any other type of medical research judged not to be scientifically or medically compatible with this study.

Other Exclusions

- 31. Are pregnant or breastfeeding.
- 32. Have known or suspected hypersensitivity reactions or intolerance to study drug or to any of the excipients (e.g., lactose), unless deemed appropriate by the investigator.

5.3. Lifestyle Considerations

Participants should refrain from consuming grapefruit, grapefruit juice, and grapefruit-containing products while on study due to their effect on cytochrome P450 (CYP)3A4.

5.4. Screen Failures

Screen failures are defined as patients who consent to participate but are not subsequently randomized to a study treatment due to inability to complete or meet the participation criteria (Sections 5.1 and 5.2) within the 28-day baseline screening period. A minimal set of screen failure information is required to ensure transparent reporting of screen failure participants to meet the Consolidated Standards of Reporting Trials (CONSORT) publishing requirements and to respond to queries from regulatory authorities. Minimal information includes demographics, screen failure details, eligibility criteria, and any serious adverse event (SAE).

If initial laboratory screening result did not meet eligibility criteria, for example absolute neutrophil count (ANC) was too low, then the test can be repeated within the 28-day screening period to confirm eligibility without being considered a screening fail. However, laboratory tests may not be repeated more than twice.

The following patients may be eligible for rescreening:

patients who have become eligible to enroll in the study as the result of a protocol amendment

patient status has changed such that the eligibility criterion that caused the patient to screen fail would no longer cause the patient to screen fail again, and patients who complete screening and meet all inclusion and exclusion requirements but are unable to be enrolled due to extenuating circumstances (such as severe weather, death in family, child illness).

The investigator should contact the Sponsor CRP prior to rescreening a patient.

5.5. Criteria for Temporarily Delaying Enrollment/Randomization/Administration of Study Intervention of a Participant

Not applicable.

6. Study Intervention(s) and Concomitant Therapy

Study intervention is defined as any medicinal product(s) intended to be administered to or used by a study participant according to the study protocol.

	Arm A		Arı	n B
Treatment	Abemaciclib	Fulvestrant	Placebo	Fulvestrant
Dose	150 mg	500 mg	Matched to abemaciclib	500 mg
Route	РО	IM	РО	IM
Schedule	BID on Days 1-28 of each cycle	C1D1 and C1D15, then on Day 1 of Cycle 2 and subsequent cycles	BID on Days 1-28 of each cycle	C1D1 and C1D15, then on Day 1 of Cycle 2 and subsequent cycles
Authorized as defined by EU Clinical Trial Regulation	Authorized and not used according to EU authorization	Authorized and not used according to EU authorization	Not authorized in EU	Authorized and not used according to EU authorization

6.1. Study Intervention(s) Administered

Abbreviations: BID = twice daily; C = cycle; D = day; IM = intramuscular; mg = milligrams; PO = orally.

Packaging and labeling

Study interventions will be supplied by the sponsor or its designee in accordance with current Good Manufacturing Practice. Study interventions will be labeled as appropriate for country requirements.

6.1.1. Selection and Timing of Doses

A cycle is defined as an interval of 28 days. The 28-day cycle length should be maintained throughout the treatment phase regardless of dose interruptions. Participants will begin dosing assigned treatment on C1D1. Every attempt should be made to maintain a 28-day +/- 7-day cycle for fulvestrant administration. When delays are required, doses should be resumed at earliest medically appropriate opportunity based on investigator judgment. Additional clinic visits may be required for administration.

Treatment will continue until progression, unacceptable toxicity, or other discontinuation criteria are met (Section 7.1).

In addition to the permitted protocol windows (see SoA, Section 1.3), a maximum of 7 days delay of a cycle start due to holiday, weekend, bad weather, or other unforeseen circumstances, but not due to AE, will be permitted and not counted as a protocol deviation. In exceptional circumstances, a delay >7 days is permitted upon agreement between the investigator and the Sponsor CRP/CRS. Response assessments should remain on the original schedule (see SoA, Section 1.3).

6.1.2. General Dosing Instructions

Assignment to either abemaciclib (Arm A) or placebo (Arm B) will be blinded to investigators and participants. Blinded study drug will be administered at a starting dose of 150 mg twice daily, and it is provided as 50 mg tablets. Blinded study drug should be taken twice daily (with at least approximately 6 hours separating doses) at the same time each day with 6-8 ounces of water. Participants should be instructed to swallow tablets whole and not chew or crush them.

In rare circumstances, if an investigator clinically determines and documents that it is in the best interest of the patient to start at a dose of blinded study drug lower than 150 mg BID, the investigator may consult with the Sponsor CRP/CRS and request approval. If the initial reduced dose is tolerated, then subsequent dose escalation is encouraged and should be discussed with the Sponsor CRP/CRS for approval.

6.2. Preparation, Handling, Storage, and Accountability

- 1. The investigator or designee must confirm appropriate storage conditions have been maintained during transit for all study intervention received and any discrepancies are reported and resolved before use of the study intervention.
- 2. Only participants enrolled in the study may receive study intervention. Only authorized study personnel may supply, prepare, or administer study intervention. All study intervention must be stored in a secure, environmentally controlled, and monitored (manual or automated) area in accordance with the labeled storage conditions with access limited to the investigator and authorized study personnel.
- 3. The investigator or authorized study personnel are responsible for study intervention accountability, reconciliation, and record maintenance (i.e., receipt, reconciliation, and final disposition records).
- 4. Further guidance and information for the final disposition of unused study interventions are provided in the Pharmacy Manual.

Investigators should consult the study drug information provided in the protocol, Investigator's Brochure, or label for the specific administration information (including warnings, precautions, contraindications, and adverse reactions).

6.3. Measures to Minimize Bias: Randomization and Blinding

Participants will be randomized at a ratio of 1:1 to Arms A and B. Randomization will be stratified by the following 3 factors:

• Geography (3 levels)

CCI

- Presence of visceral metastases (2 levels)
 - Yes, or
 - o No
- Duration on prior adjuvant/metastatic CDK4 & 6 inhibitor-based regimen (2 levels)

Assignment to treatment groups will be determined by a computer-generated random sequence using the IWRS. Upon obtaining informed consent, site personnel should access the IWRS, which will assign a patient number. Participants who meet all criteria for enrollment will be randomly assigned to treatment.

Arms A and B will be blinded to participants and investigators.

The Sponsor will collect and store all tumor images throughout the study. An independent review of imaging measurements will be performed by an independent panel of radiologists. In addition, a secondary PFS analysis based on independent central review will be conducted.

Participants randomized to the control group (Arm B) will not be permitted to cross over to the experimental group (Arm A). If a participant discontinues study treatment and knowledge of the participant's treatment assignment is deemed essential to the selection of the participant's next treatment regimen, the investigator may consult with the Sponsor CRP/CRS and request unblinding to guide further post-discontinuation therapies. There are no restrictions to post-discontinuation therapy.

Interim analyses for safety and efficacy/futility will be conducted under the guidance of an independent data monitoring committee (DMC). Refer to Section 10.1.5 for additional details.

For safety and efficacy/futility analyses assigned to the DMC, only the designated Statistical Analysis Center (SAC), which is independent of the Sponsor, will perform analyses on unblinded data, that is, an aggregate database with actual treatment assignments. At the request of the Sponsor, the SAC may provide pooled summary reports to the Sponsor (for example, a summary of AEs across the study). These reports will not include treatment arms.

Early access to PK Data

To support timely exposure-response analyses, PK analyses will be conducted prior to the first efficacy interim analysis. Periodic transfers for review of data relevant to PK analyses, including dosing and bioanalytical results, will be performed. An early PK analysis will be performed when the majority of treated participants have completed their final PK sample collection visit, and prior to the first efficacy interim analysis. This early PK analysis will be performed by an independent team of PK analysts, and the results will not be shared with the study team until the trial is fully unblinded. Protocols will be in place to maintain the blind, including the use of

- separate restricted data containers
- aliased patient identifiers (IDs), and

datasets containing data required for population PK analysis only (specifically, no efficacy data).

6.3.1. Emergency Unblinding

In case of an emergency, the investigator has the sole responsibility for determining if unblinding $-(z(z \leq z (.z \bullet ... (z `` \bullet ... (' (z z ... \geq i z \leq z (z - ... (\bullet always be the first consideration in making such a determination. If the investigator decides that unblinding is warranted, the investigator should make every effort to contact the Sponsor CRP/CRS prior to <math>\bullet \circ \geq : :(z(z \leq z (.z \bullet ... (z `` \bullet ... (z `` \bullet ... (' (.z \in ... (z `` \bullet ... (' (.z \in ... (' (.z \in ... (' (.z \in ... (' (.z \in ... (' (... (' (.z \in ... (' (' (... (' (' (... (' (' (... (' (' (... (' (' (... (' (' (... (' (' (' (... (' (' (' (' (' (.$

Emergency unblinding for AEs must be performed through the IWRS. This option may be used '-(".(. $z \leq z$ ($z \leq ...$ ($z \geq$ ($z \geq ...$ (z

All calls resulting in an unblinding event are recorded and reported by the IWRS.

If the investigator or participant becomes unblinded, that participant will be discontinued from study intervention and will undergo post-discontinuation follow-up. Long-term follow-up procedures will be followed until death, loss of follow-up, withdrawal of consent, or study completion. In cases in which there are ethical reasons for the participant to remain on the study intervention in the event of unblinding, the investigator must obtain specific approval from the Sponsor CRP/CRS for the participant to continue in the study.

6.3.2. Inadvertent Unblinding

Every effort will be made to blind both the participant and the investigator to the identity of the treatment, but the inadvertent unblinding of a participant may occur. If an investigator, site personnel, or participant is inadvertently unblinded, the unblinding will not be sufficient cause for the participant to be discontinued from study intervention or excluded from study analyses. In cases in which there are ethical reasons for the participant to remain on the study intervention in the event of unblinding, the investigator must obtain specific approval from the Sponsor CRP/CRS for the participant to continue in the study.

6.4.2. Fulvestrant

Fulvestrant will be administered under medical supervision by the investigator or designee. The investigative site will record the date, time, and dose in the source documents and CRF. The site will also record any dose adjustments and reason for adjustment. If the dose was not administered, the site will document the reason.

6.5. Dose Modification

In exceptional cases of planned delays (including but not limited to vacation or holidays), additional study drug may be dispensed.

When treatment is delayed, if possible and appropriate, patients should resume within the same treatment cycle. If not possible, then every effort should be made to resume on the first day of the next scheduled cycle. In rare circumstances, if the participant has clinical benefit without disease progression and is recovering from toxicity, a delay of >28 days may be permitted. Such circumstances must be discussed with the Sponsor CRP/CRS. All dose modifications should be documented, including a clear rationale for the modification.

U.(. ...' (AC($\geq z$ (• (•.($\geq' \leq ...\geq$ ('"(".(\$ponsor CRP/CRS.)))

6.5.1. Blinded Study Drug

Management of some adverse reactions may require dose interruption and/or dose reduction. When dose reduction is necessary, decrease the dose by 50 mg at a time. Discontinue blinded study drug for patients unable to tolerate 50 mg BID. If blinded study drug must be discontinued, a participant may continue to receive fulvestrant.

Refer to the tables below for further details on dose modification and management. Dose Reduction Guidelines

Dose Adjustment	Blinded Study Drug Dose	Frequency
Starting dose	150 mg	BID
First dose reduction	100 mg	BID
Second dose reduction	50 mg	BID

Abbreviation: BID = twice a day.

6.5.1.1. Blinded Study Drug Dose Adjustments for Treatment-Emergent, Related* Adverse Events

The table below provides guidance for the management of treatment-emergent, related (i.e., with reasonable causal relationship with blinded study drug) AEs. An investigator may use discretion and suspend or reduce doses without meeting one of the criteria below and this would not be considered a protocol deviation, though rationale should be documented.

*Related means there is a reasonable causal relationship with blinded study drug.

Toxicity Type	Severity	Dose Suspension	Dose Reduction	
	Grade 1 or 2	Not required		
Hematologic Toxicity	Grade 3	Suspend until toxicity resolves to Y z≥.(A	Not required	
	Recurrent Grade 3, or Grade 4	Suspend until toxicity resolves to Y z≥.(A	Resume at next lower dose level	
Patient Requires Blood Cell Growth Factors Additional guidance for use of growth factors is in Section 6.8.1	Regardless of severity	Suspend until toxicity resolves to at least Grade 2 and a minimum of 48 hours after growth factor administration	Resume at next lower dose unless the dose was already reduced for the toxicity that led to the use of the growth factor (that is, a second dose reduction not required)	
	Grade 1 or 2	Not requ	ired	
Nonhematologic Toxicity Excluding Diarrhea, ALT/AST Increased, Interstitial Lung Disease/Pneumonitis, and VTE (see below) Additional guidance for renal monitoring is in Section 8.2.4 and for VTE Section 8.2.5.	Persistent or recurrent Grade 2 that does not resolve with maximal supportive measures within 7 days to baseline or Grade 1 or Grade 3 or 4	Suspend until toxicity resolves to baseline or Grade 1	Resume at next lower dose level	
Diarrhea	Grade 1	Not required		
Additional guidance for diarrhea management is in Section 6.8.3.	in $\begin{array}{ c c c c c }\hline Grade 2 \text{ that does} & Suspend until toxicity resolves to} & Y z \ge . (< within 24 hours & Y z \ge . (<) \end{array}$		Not required	

Toxicity Type	Severity	Dose Suspension	Dose Reduction
	Grade 2 that persists or recurs after resuming the same dose despite maximal supportive measures or Grade 3 or 4 or Requires hospitalization	Suspend until toxicity resolves to Y z≥. (<	Resume at next lower dose level
	Grade 1 or 2	Not requ	ired
ALT/AST Increased	Persistent or recurrent Grade 2, or Grade 3	Suspend until toxicity resolves to baseline or Grade 1	Resume at next lower dose level
See Section 8.2.3 for additional guidance for hepatic monitoring and Section 8.2.3.1 for special hepatic safety data collection.	Y z≥. (Awith total bilirubin >2×ULN, in the absence of cholestasis, or Grade 4	Discontinue blinded study drug	
	Grade 1 or 2	Not requ	ired
VTE Additional guidance for VTE monitoring is in Section 8.2.5.	Grade 3 or 4	Suspend and treat. Resume when the patient is clinically stable	Not required
	Grade 1 or 2	Not requ	ired
Interstitial Lung Disease/Pneumonitis Additional guidance for ILD/pneumonitis monitoring is in Section 8.2.6.	Grade 2 that persists or recurs despite maximal supportive measures and does not return to baseline or Grade 1 within 7 days.	Suspend until toxicity resolves to baseline or $Y z \ge1$ Resume at lower dose	
	Grade 3 or 4	Discontinue blind	ed study drug

Abbreviations: ALT = alanine aminotransferase; AST = aspartate aminotransferase; ILD = interstitial lung disease; ULN = upper limit of normal; VTE = venous thromboembolic event.

Note: Determination of persistent events will be at the discretion of the investigator. Recurrent toxicity refers to the same event occurring within 8 weeks (as measured from the stop date of the first event). As general guidance, for a participant who experiences a new episode of Grade 3 hematological toxicity more than 8 weeks from a previous episode of the same Grade 3 toxicity, the investigator may consider resuming the same dose if the participant satisfies the following conditions:

s $z \bullet Q$ ("... $\bullet z \circ$ "' $\leq z \phi \leq$ (2Y $z \geq ...$ (A) (\geq '"("z (' \bullet ... frame

absence of serious infections ongoing benefit

6.5.1.2. Re-escalation Criteria for Blinded Study Drug

If the blinded study drug dose is reduced for an apparent treatment-related toxicity, the dose need not be re-escalated, even if there is minimal or no toxicity with the reduced dose. However, if the $z'...(Q.Z...(z(...) \le \le \le) \le ...(-...) (A(....) \le ...("...("...) (..$

6.5.2. Fulvestrant

Fulvestrant dose adjustments will be determined by the investigator in accordance with the approved product labels. Dose may be re-escalated at the discretion of the investigator and after consultation with the Sponsor CRP/CRS. For patients with moderate hepatic impairment (defined as Child-Pugh Class B), including any patient who develops moderate hepatic impairment during study treatment, fulvestrant 250 mg should be administered intramuscularly into the buttock slowly (1 to 2 minutes) as one 250-mg injection. In the event that fulvestrant must be discontinued, a participant may continue to receive blinded study drug.

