To compare PRO measures of fulvestrant with or	SF worst pain item				
without abemaciclib	Time to deterioration in physical function via				
	the EORTC IL-19				
To characterize the pharmacokinetics (PK) of	Concentrations of abamagialib				
abemaciclib in combination with fulvestrant					

Objectives and Endpoints:

Abbreviations: BICR = blinded independent central review; CBR = clinical benefit rate; DCR = disease control rate; DoR = duration of response; EORTC IL-19 = European Organisation for Research and Treatment of Cancer Item Library 19; mBPI-SF = modified Brief Pain Inventory-short form; ORR = objective response rate; OS = overall survival; PRO = patient-reported outcome; PFS = progression-free survival; RECIST = Response Evaluation Criteria in Solid Tumors; SAE = serious adverse event; TEAE = treatment-emergent adverse event.

Overall Design

postMONARCH is a Phase 3, global, multicenter, randomized, double-blind, placebo-controlled study in participants with HR+, HER2- advanced or metastatic breast cancer. This study will enroll adults who experienced disease progression on a CDK4 & 6 inhibitor and an AI in the first-line setting or relapse on/after a CDK4 & 6 inhibitor with ET in the adjuvant setting. The intervention arms include:

- Arm A: abemaciclib and fulvestrant (Investigational)
- Arm B: placebo and fulvestrant (Control)

Randomization will be 1:1 and stratified by the following factors:

- geography: CCI
- presence of visceral metastases: yes or no (visceral includes lung, liver, brain, pleural, and peritoneal involvement), and
- duration on prior adjuvant/metastatic CDK4 & 6 inhibitor-based regimen (2 levels):

The primary endpoint of PFS will be based upon investigator assessment.

Duration of Treatment:

Participants will be treated until disease progression or other discontinuation criteria are met.

Study Population

Participants are eligible to be included in the study only if all the following criteria apply:

- ≥18 years of age (or of an acceptable age according to local regulations, whichever is older) at the time of signing the informed consent
- have a diagnosis of HR+, HER2- breast cancer
- have either advanced disease not amenable to curative surgical treatment or metastatic disease
- have radiologic evidence of disease progression or recurrence either
 - on treatment with a CDK4 & 6 inhibitor plus AI as initial therapy for advanced disease, or

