2.3.2. Benefit Assessment

All participants will receive a known active therapy for HR+, HER2- MBC, either abemaciclib or fulvestrant. Both abemaciclib and fulvestrant are approved as single agents for the treatment of MBC (abemaciclib and fulvestrant package inserts). Treatment with abemaciclib plus fulvestrant may result in improved clinical benefit compared to fulvestrant plus placebo.

Based on known data, treatment with the combination of abemaciclib and fulvestrant is expected to be well tolerated and to delay disease progression. Prolonged disease control may also delay the need for cytotoxic chemotherapy.

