6.8.5. Medications and therapies not permitted

With the exceptions listed in the sections below, therapies for cancer (including specifically aromatase inhibitors, anti-estrogens other than fulvestrant, chemotherapy, and immunotherapy) will not be permitted while patients are on study treatment. Use of megestrol acetate as an appetite stimulant is not permitted due to anti-estrogen effects.

7. Discontinuation of Study Intervention and Participant Discontinuation/Withdrawal

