4.1.1. Definitions and Conventions

Study drug refers to abemaciclib or placebo.

Study treatment refers to abemaciclib plus fulvestrant or placebo plus fulvestrant.

The **date of randomization** is the date the patient was randomly assigned to study treatment using the interactive web response system.

The date of first dose is the date of the first dose of study drug or fulvestrant.

The **baseline value of a safety assessment** is the last value observed prior to the first dose of study drug or fulvestrant.

The **baseline value of an efficacy assessment** is the last value observed prior to the date of randomization. If a patient's first assessment occurs after randomization but prior to the first dose, this assessment will be used as the baseline.

The study day of a safety event or assessment will be calculated as:

- the difference between the date of the event or assessment and the date of first dose plus 1 for all events or assessments occurring on or after the day of first dose. For example, if an event occurs on 08 March 2016 and the date of first dose was 06 March 2016, the study day of the event is 3.
- the difference between the date of the event or assessment and the date of first dose for all events or assessments occurring before the day of first dose. For example, if an event occurs on 05 March 2016 and the date of first dose was 06 March 2016, the study day of the event is -1.

The study day of an efficacy event or assessment will be calculated as:

• the difference between the date of the event or assessment and the date of randomization plus 1 for all events or assessments occurring on or after the date of randomization.

• the difference between the date of the event or assessment and the date of randomization for all events or assessments occurring before the date of randomization.

One **month** is defined as 365/12 days.

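### Protocol 6.5.2 lets an Arm B participant stay on placebo as the only study medication after fulvestrant stops, which conflicts with the unqualified benefit statement in 2.3.2

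*Protocol*

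**What the plan says.** Protocol 6.5.2, on fulvestrant dose changes, ends with this rule: "In the event that fulvestrant must be discontinued, a participant may continue to receive blinded study drug". It applies to both arms alike. The section asks for sponsor consultation on re-escalating fulvestrant, but not on this decision.

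Arm B is placebo plus fulvestrant (Protocol 1.1 and 4.1). SAP 4.1.1 says that study drug "refers to abemaciclib or placebo". Protocol 6.3 adds: "Arms A and B will be blinded to participants and investigators".

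The benefit assessment in Protocol 2.3.2 says: "All participants will receive a known active therapy for HR+, HER2- MBC, either abemaciclib or fulvestrant".

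Two further provisions apply while the participant stays on blinded drug. Protocol 6.8.5 says that cancer therapies outside the regimen "will not be permitted while patients are on study treatment". Protocol 6.3 offers non-emergency unblinding on this condition: "If a participant discontinues study treatment and knowledge of the participant's treatment assignment is deemed essential to the selection of the participant's next treatment regimen".

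**The concern.** Fulvestrant is the only active component of the control regimen. Once it stops, the same permission has different meanings in the two arms: abemaciclib alone in Arm A, placebo alone in Arm B. An Arm B participant continuing under 6.5.2 receives neither of the two drugs that 2.3.2 names.

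What is at stake is mainly participant protection and the accuracy of the benefit-risk text. Site and participant must decide whether to continue without the one fact that most affects the choice, namely whether the remaining drug is active. The stated route to that fact opens only after they have decided to stop. There is also a smaller reporting matter. SAP 4.7.1 summarises exposure to each drug separately, so time on blinded drug alone would not be visible in the report.

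**Working it through.** The plan gives no figure on this point, so the check is a reading of the sections against each other.

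**Step 1. What the rule leaves in each arm.**

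| Component stopped | Protocol section | Arm A continues on | Arm B continues on |
|---|---|---|---|
| Blinded study drug | 6.5.1 | fulvestrant | fulvestrant |
| Fulvestrant | 6.5.2 | abemaciclib | placebo |

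Only the last cell has no active study medication. The mirror rule in 6.5.1 does not have the problem.

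**Step 2. Does another section prevent that cell?**

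- Protocol 7.1 lists reasons to discontinue study intervention. Stopping fulvestrant is not among them. Investigator decision and participant request are, and both are made blind to arm.
- Protocol 6.3 makes non-emergency unblinding available once study treatment is discontinued, and rules out crossover from Arm B to Arm A.
- Protocol 6.3.1 covers emergencies. A participant who is unblinded is taken off study intervention unless the sponsor approves otherwise for ethical reasons, so it is not an ordinary route to informed continuation.
- Protocol 6.6 ends placebo by rule, but only in the continued-access period after study completion.

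None of these closes the gap.

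**Step 3. Is such a participant still on study treatment?** The bar in 6.8.5 and the unblinding route in 6.3 both depend on the answer. The overview in Protocol 1.3 times the short-term follow-up visit from the decision to stop all study treatment, which implies that a participant on blinded drug alone is still on treatment. SAP 4.1.1 defines study treatment as the two-drug combination, which leaves the status of a participant on one component unclear. No section states it directly.

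**Step 4. How many?** The documents give no rate of fulvestrant discontinuation. As an assumption only, suppose 1% to 5% of the 350 participants stop fulvestrant before blinded drug, equally in both arms, and all of them stay on blinded drug. With 1:1 allocation the placebo-only number is rate × 350 / 2:

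- 0.01 × 350 / 2 = 1.75
- 0.05 × 350 / 2 = 8.75

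That is about 2 to 9 participants. Because 6.5.2 allows continuation but does not require it, each figure is the most that its assumed rate could give under equal rates by arm. The range has no source in the documents, and the conflict between 6.5.2 and 2.3.2 does not depend on it.

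**The case against.** **The benefit statement may describe the assigned regimen.** Every Arm B participant is assigned fulvestrant, and 2.3.2 does not promise active therapy after a drug has to be stopped. This reading is possible. But the sentence is unqualified and forms part of the benefit-risk case, so if that is the meaning the protocol should say so.

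**Continuing is optional and there are exits.** This stands. A reader might infer that participants are left untreated with alternatives prohibited; the documents do not support that. Under 7.1 study intervention ends on the participant's request, on the investigator's decision, or when another effective agent is needed. Under 6.8.1 clinical deterioration that requires other systemic antitumor therapy is cause to stop. Under 6.3 there is no restriction on therapy afterwards, and unblinding can be requested to guide it. Site and participant also know that fulvestrant has stopped and that what remains is either abemaciclib or placebo. What remains of the point is that they choose without knowing which.

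**No one with known progression is kept on placebo.** This also stands. Evidence of progressive disease requires discontinuation under 7.1. Nor does the 8- or 12-week scan interval by itself set how long placebo-only time lasts, since clinic visits are every 2 weeks in Cycles 1 and 2 and monthly from Cycle 3.

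**Other treatment may continue.** Placebo alone here refers to study medication. Hormone suppression required at entry for some participants (Protocol 5.1) and bone-modifying agents (6.8.2) would carry on.

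**The estimand is not breached.** A reader might infer that the comparison becomes abemaciclib versus placebo, outside the treatment condition and biased toward Arm A. The treatment condition in Protocol 3 refers to Section 6 for dose modification, and 6.5.2 belongs to that section. The primary analysis is by assigned arm in the ITT population. No calculation shows a material effect on the hazard ratio.

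**SAP 4.7.1 already reports duration, omissions and reasons for each drug by arm.** This is true, so the added row is optional.

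**Conclusion.** The point holds as a conflict between a stated rule and a stated assurance. Protocol 6.5.2 permits placebo as the only study medication in Arm B, no other section prevents it, and 2.3.2 as written is untrue for a participant who continues that way. The decision to continue is voluntary and reversible, but it is made blind to whether the remaining drug is active.

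The number affected is unknown and probably small. The illustration of about 2 to 9 participants rests on an assumed rate and should not be cited as an estimate. No breach of the estimand and no material bias is shown, and the point changes no design figure. It deserves correction because it bears on participant protection and on the accuracy of the benefit-risk text, and because the correction is cheap.

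**What to change.** Reconcile Protocol 2.3.2, 6.3, 6.5.2, 6.8.5 and 7.1 so that they agree on three things for a participant who must stop fulvestrant: whether that participant is still on study treatment, which therapy and unblinding provisions then apply, and whether the benefit statement describes the assigned regimen or treatment throughout. The benefit statement and the rule should match. Which of them changes, and what the clinical rule is, is for the sponsor to decide.

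Optionally, add to the SAP 4.7.1 exposure summary, by arm, the number of participants who stopped fulvestrant before blinded drug and their days on blinded drug alone. Those days could be counted from the first scheduled fulvestrant date not given after permanent discontinuation to the last blinded dose. Protocol 6.4.1 and 6.4.2 already have the dosing dates recorded in the CRF.

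The cost is a protocol wording change, a communication to sites, and one derived table row if that option is taken. No visits, participants or events are added. The sponsor does have to settle a rule that may affect only a few people.
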